6.1.4 Guidelines for continuation of treatment

For guidelines for continuation of treatment, refer to Section 6.3 Dosing modifications.

Patients who permanently discontinue one of the study drugs for any reason other than disease progression may continue the other study drug as part of the trial therapy at the investigator's discretion until disease progression, unacceptable toxicity, death or discontinuation from study treatment due to any other reason and should follow the protocol safety and efficacy assessments as scheduled. After discontinuing all study treatment, further treatment is left to the physician's discretion.

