6.3.1.4 Alpelisib

For patients who do not tolerate the protocol-specified dosing schedule, dose adjustments are permitted in order to allow the patient to continue the study treatment. All dose modifications must be based on the worst preceding toxicity as graded by the NCI Common Terminology Criteria [NCI-CTCAE v4.03]. If the administration of alpelisib is interrupted for reasons other than toxicity, then treatment with alpelisib may be resumed at the same dose.

A maximum of 2 dose reductions of alpelisib from the recommended starting dose may be allowed before considering discontinuation of alpelisib treatment.

Please refer to Table 6-2 and Table 6-3 for guidance.

Table 6-2 Dose reduction sequential steps for alpelisib

Alpelisib dose level	Dose and schedule	Number of tablets & strength
Starting dose	300 mg/day continuously	1 x 200 mg tablet and 2 x 50 mg tablet
Dose level -1	250 mg/day continuously	1 x 200 mg tablet and 1 x 50 mg tablet
Dose level -2	200 mg/day continuously	1 x 200 mg tablet

Recommendations for dose reduction or dose interruption of alpelisib in the management of adverse reactions are summarized in Table 6-3. Adverse events for alpelisib are graded according to (Common Terminology Criteria for Adverse Events (CTCAE) v4.03 since this version is more objective with regards to hyperglycemia grading since it is based on laboratory values. Clinical judgment of the treating physician, including confirmation of lab values if deemed necessary, should guide the management plan of each patient based on individual benefit/risk assessment.

However, treatment must be discontinued as indicated in Table 6-3.

After treatment is resumed at a lower dose:

- If the same toxicity recurs with the same severity, then the next treatment re-initiation must resume at a lower dose irrespective of duration.
- Once the alpelisib dose has been reduced, no re-escalation will occur, even upon resolution of AE.

If a participant requires a withholding of alpelisib dose, the participant should continue combination drug, per investigator discretion. All scheduled assessments will continue to be performed as per protocol.

If administration of alpelisib dosing is held for more than 28 days, then alpelisib must be permanently discontinued. Grade 4 adverse events will lead to permanent discontinuation, irrespective of recovery time, unless otherwise specified. Patients requiring more than 2 dose reductions for alpelisib should be permanently discontinued.

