Table 6-3 Criteria for interruption and re-initiation of alpelisib treatment

Dose Modifications for alpelisib as specified below. Fulvestrant and letrozole may be continued while alpelisib dose is being held, at the investigators discretion, and as specified in Section 6.3.1

Worst toxicity – CTCAE Grade (value)

Dose Modifications for alpelisib

Investigations (Fasting Glucose or Random blood glucose)

Hyperglycemia (see also Section 6.3.2.1.3)

Consultation with a diabetologist or healthcare provider experienced in the management of hyperglycemia is highly recommended for better assessment and management of alpelisib-induced hyperglycemia. Always recommend/reinforce on lifestyle changes as per American Diabetes Association (ADA) and/or European Association for the study of Diabetes (EASD), i.e. exercise and dietary advice (e.g. controlled carbohydrate intake, high fiber, low process food intake. Three macronutrient balanced meals and 2 optional small snacks rather than one large meal).

Note: this table provides dose management recommendations. Local standard clinical practice may be followed for monitoring and managing hyperglycemia. However dose reduction should only be based on FPG. As metformin is widely available, it is an appropriate choice as initial therapy for alpelisib-induced hyperglycemia. However, SGLT2 inhibitors as per local regulations, are acceptable as well and may be administered alone or in combination with metformin. The use of metformin XR can be considered as a suitable alternative to metformin IR, alone or in combination with an SGLT2 inhibitor, particularly for participants with at least one risk factor for the development of severe hyperglycemia, at the discretion of the Investigator and as per local regulations. (Jabbour and Ziring, 2011).

Refer to Section 6.3.2.1.3 ("Guidelines for the treatment of alpelisib induced hyperglycemia") for additional details regarding the use of metformin XR and/or SGLT2 inhibitors. In case of intolerance to or unavailability of metformin, investigator's judgment should be exercised and as per local regulations, other oral anti-diabetic agents such as thiazolidinediones or dipeptidyl peptidase-4 inhibitors can be used.

SGLT2 inhibitor may increase the risk of euglycemic diabetic ketoacidosis and therefore, monitoring with serum / urine ketones and consultation with a healthcare expert experienced in hyperglycemia management or a diabetologist should be considered.

Grade 1

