Grade 3 (Increase of ≥7 stools per day over baseline; hospitalization indicated; severe increase in ostomy output compared to baseline; limiting self-care ADL)	Omit dose until resolved to ≤ Grade 1, then ↓ 1 dose level
OR	Manage according to local standard of care medical management, including electrolyte monitoring, administration of antiemetics and antidiarrhoeal

Worst toxisity CTCAE Grade (value)	Doca Madifications for alpaliaib	
Worst toxicity – CTCAE Grade (value)	Dose Modifications for alpelisib medicinal products and / or fluid replacement and	
Severe abdominal pain; peritoneal signs	electrolyte supplements as clinically indicated.	
	For Grade 3 colitis consider additional treatment, such as steroids.	
Grade 4 (Life-threatening consequences; urgent intervention indicated)	Discontinue subject from treatment.	
	Manage according to local standard of care medical management, including electrolyte monitoring, administration of antiemetics and antidiarrhoeal medicinal products and /or fluid replacement and electrolyte supplements, as clinically indicated.	
Investigations (Pancreatic)		
Pancreatitis		
Grade 2 (enzymatic elevation or radiologic findings only)	Omit dose until resolved to Grade ≤ 1, then resume treatment at ↓ 1 dose level. If toxicity recurs, permanently discontinue patient from alpelisib	
Grade 3	 Omit dose until complete resolution of symptoms 	
For patients deriving clinical benefit upon investigator's judgement:	and lipase resolved to Grade ≤ 1, then resume treatment at ↓ 1 dose level. Only 1 dose reduction is allowed.	
	 If recovery to ≤ Grade 1 is greater than 28 days, the patient must be discontinued from the study. 	
For other patients:	 If toxicity reoccurs, permanently discontinue patient from alpelisib 	
	Permanently discontinue patient from alpelisib	
Grade 4	Permanently discontinue patient from alpelisib	
Stomatitis/Oral mucositis (see also Appendix 3)		
Grade 1/Tolerable Grade 2	Maintain dose level	
	Non-alcoholic or salt water mouth wash	
Intolerable Grade 2 or Grade 3	First occurrence: hold until ≤ Grade 1 and ↓ 1 dose level (if stomatitis is readily manageable with optimal management, re-introduction at the same level might be considered at the discretion of the investigator).	
	Second occurrence: hold until ≤ Grade 1 and ↓ 1 dose level.	
Grade 4	Permanently discontinue patient from alpelisib	
Skin and subcutaneous tissue disorders		

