6.3.2.1.4 Follow-up on amylase or lipase elevation (≥ CTCAE Grade 3)

Patient with amylase or lipase elevation \geq CTCAE Grade 3 must be tested weekly (or more frequently if clinically indicated) until \leq Grade 1 (or baseline). After resumption of dosing, continue to test weekly for one additional cycle. If no reoccurrence of \geq Grade 2 event, continue monitoring every cycle.

An exception to these follow-up guidelines will be made for cases of isolated amylase elevations in which amylase fractionation demonstrates that pancreatic amylase is \leq Grade 1. In such cases, total amylase and fractionated amylase should be monitored weekly (or more frequently if clinically indicated) for 4 weeks. If pancreatic amylase remains \leq Grade 1, subsequent monitoring must be performed at least every 4 weeks (or more frequently if clinically indicated).

Patients who discontinue study treatment due to pancreatic toxicity must be monitored weekly (or more frequently if clinically indicated) until the event resolves to \leq grade 1 or stabilization occurs (no CTCAE grade change over 4 weeks).

If amylase and/or lipase elevations are accompanied by new or progressive unexplained abdominal symptoms such as severe pain or vomiting, withhold study treatment, then perform diagnostic procedures (e.g., abdominal CT scan or ultrasound) to exclude pancreatic pathology.

See also dose modification guidelines described in Table 6-3.

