7.1.5 Discontinuation of study treatment

Patients may voluntarily discontinue from the study treatment for any reason at any time. They may be considered withdrawn if they state an intention to withdraw, fail to return for visits, or become lost to follow-up for any other reason.

The investigator may discontinue study treatment for a given patient if he/she believes that continuation would be detrimental to the patient's well-being.

Patients may voluntarily withdraw from the study or be dropped from it at the discretion of the investigator at any time.

For patients who discontinue treatment during the Core Phase for reasons other than documented disease progression, death, lost to follow-up, or withdrawal of consent, tumor assessments must continue to be performed every 12 weeks until documented disease progression, death, lost to follow-up, or withdrawal of consent. This does not apply to the

Extension Phase; once the patient enters the Extension Phase, tumor imaging is no longer required per the study schedule.

Patients may be withdrawn from the study treatment if any of the following occur:

- Adverse event or laboratory abnormalities as indicated in Section 6.3
- Lost to follow-up
- Physician decision
- Progressive disease
- Protocol deviation
- Study terminated by sponsor
- Technical problems

Patients must be withdrawn from the study treatment if any of the following occur:

- Pregnancy
- Death
- Subject/Guardian decision

Patients who discontinue study treatment should undergo an End of Treatment (EOT) visit followed by a 30 day safety follow-up. At EOT (during the Core Phase), a tumor assessment scan should be performed if the previous scan is older than 30 days.

The investigator or his/her delegate must also contact the IRT to register the patient's discontinuation from study treatment.

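### One row of Table 6-3 takes a benefiting Grade 3 pancreatitis patient out of the study, where the related rules stop only alpelisib or study treatment

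*Protocol*

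**What the plan says.** Protocol Table 6-3, in section 6.3.1.4, is titled "Criteria for interruption and re-initiation of alpelisib treatment", so its scope is alpelisib dosing. Its Grade 3 pancreatitis row splits patients in two. One group is introduced by "For patients deriving clinical benefit upon" the investigator's judgement. These patients hold alpelisib until symptoms and lipase recover and then resume one level lower, but "If recovery to ≤ Grade 1 is greater than 28 days, the patient must be discontinued from the study". For the other Grade 3 patients, and for Grade 4, the instruction is to "permanently discontinue patient from alpelisib".

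Elsewhere the protocol treats the same or a closely related situation as follows.

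- Section 6.3.1.4, general rule: "If administration of alpelisib dosing is held for more than 28 days, then alpelisib must be permanently discontinued".
- Section 6.1.4: "Patients who permanently discontinue one of the study drugs for any reason other than disease progression may continue the other study drug", with safety and efficacy assessments kept on schedule.
- Section 6.3.2.1.4: "Patients who discontinue study treatment due to pancreatic toxicity must be monitored weekly" until the event resolves or stabilises.
- Section 7.1.5, for Core Phase patients who stop treatment for reasons other than progression, death, loss to follow-up or withdrawn consent: "tumor assessments must continue to be performed every 12 weeks until documented disease progression". Sections 4.3 and 7.1.8 say the same in substance, and 7.1.9 does so for survival.

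Protocol 10.4.3 and SAP 2.5.3 define failure on the primary endpoint as progression, death or leaving the study before six months. Neither names stopping treatment as a failure.

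**The concern.** The row gives the most drastic instruction to a patient who is neither the sickest nor the one with least to gain. Taken at its word, a benefiting Grade 3 patient with slow recovery leaves the trial, while a Grade 4 patient and a non-benefiting Grade 3 patient lose one drug and stay in follow-up.

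Two things follow if a site obeys the row literally. The patient loses the option in 6.1.4 of continuing fulvestrant or letrozole within the trial. Tumour follow-up also ends, and if this falls before six months a patient without progression is counted as a failure in the primary analysis because of a dosing rule rather than the disease.

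**Working it through.** **Step 1. Set the instructions side by side.**

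| Situation | What is stopped | Place |
|---|---|---|
| Pancreatitis Grade 2, recurring | alpelisib | Table 6-3 |
| Pancreatitis Grade 3, benefiting, recovery over 28 days | participation in the study | Table 6-3 |
| Pancreatitis Grade 3, benefiting, recurring after resumption | alpelisib | Table 6-3 |
| Pancreatitis Grade 3, other patients | alpelisib | Table 6-3 |
| Pancreatitis Grade 4 | alpelisib | Table 6-3 |
| Any alpelisib hold over 28 days | alpelisib | 6.3.1.4 |

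One entry is out of line with the rest. Broken table rows in the extracted text do not explain it: only the benefiting Grade 3 patients have a hold-and-resume path with a recovery clock that could exceed 28 days.

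**Step 2. Are the two terms interchangeable?** The protocol keeps them apart. Section 7.1 sends a patient who stops study treatment to an end-of-treatment visit and then to follow-up visits, but sends a patient who leaves the study to a final evaluation visit. Section 7.1.10 also lists the two separately. A literal reader therefore has grounds to end follow-up.

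**Step 3. What has to happen for the endpoint to be touched.** All of the following are needed: Grade 3 pancreatitis; a judgement that the patient is benefiting; recovery taking more than 28 days (4 weeks); literal removal from the study; no progression or death; and all of it before six months, which 10.4.3 sets at 24 weeks ± 1 week. Onset must then come before about week 24 − 4 = 20. Exclusion criterion 18 (recent acute or any chronic pancreatitis) and inclusion criterion 15 (fasting lipase not above the upper limit of normal) make the event less likely still.

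**Step 4. Size.** Inputs: null proportion 0.30 (Protocol summary, Data analysis); n = 112 per cohort, one-sided 2.5%, and power of at least 90% at a true rate of 0.45 (10.8); rejection at 44 or more of 112 (10.4.2).

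The plan's own figures come first, from the exact binomial tail P(X ≥ 44 | n = 112, p):

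- p = 0.30: 0.0225, below 0.025.
- p = 0.45: 0.9055, so the stated power reproduces.

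The Clopper-Pearson lower limit is the 2.5th percentile of Beta(k, n − k + 1):

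- k = 44: 44/112 = 39.3%, Beta(44, 69), lower limit 30.19%. Null rejected.
- k = 43: 43/112 = 38.4%, Beta(43, 70), lower limit 29.36%. Null not rejected.

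One patient wrongly scored as a failure lowers the observed proportion by 1/112 = 0.89 percentage points. It changes the decision only if the cohort would otherwise have had exactly 44 successes.

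**The case against.** The best defence is that the protocol already settles the matter. Section 7.1.5 lists toxicities indicated in Section 6.3 among the reasons for withdrawal from study treatment, the sentence leading into Table 6-3 speaks of discontinuing treatment, and the table's column concerns alpelisib dose changes. A careful site would see a treatment stop and keep scanning. This stands as far as it goes: it makes a drafting slip the likeliest explanation and literal removal less likely. It does not remove the conflict, because the row is a specific and mandatory instruction using a term that the protocol distinguishes from stopping treatment.

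A second defence is timing. Enrolment was complete as of 14-Dec-2020, each cohort's primary analysis falls six months after its last patient starts, and the current text dates from March 2023. In the Extension Phase no protocol imaging is required. This also stands: changing the wording cannot alter six-month data already collected. Version 06 still governs dosing in the Extension Phase, however, and there the literal reading would deny the patient the partner drug within the trial.

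A third is that the sponsor may have meant both drugs to stop after prolonged severe pancreatitis. Section 6.3.2.1.4 refers to study treatment, and Grade 4 diarrhoea in the same table ends treatment generally. This is possible, and the fix allows for it. It still does not support removal from the study.

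Finally, 7.1.11 includes an adverse event among the reasons for which follow-up may end. That is a list of disposition reasons. It does not instruct anyone to end follow-up because treatment stopped, and 7.1.5 and 7.1.8 state the operative rule.

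**Conclusion.** The row is wrong as written, and the point is minor. The contradiction can be seen on the page; the endpoint consequence is a possibility that depends on literal reading and on a rare chain of events. If it occurred, it would count against the treatment. Zero or one patient in a cohort is an assumption, since the documents give no rate for this event. At one patient the shift is 0.89 points at n = 112, decisive only at 44 against 43.

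A reader might infer that the primary result was biased or that power was lost. The documents do not support either: they give no event rate from which a power loss could be computed, and nothing shows that a patient was removed or scored in this way. The Kaplan-Meier six-month PFS estimate in SAP 2.7.2 gives a partial cross-check, because SAP 2.7.3 censors such a patient instead of failing them; the hypothesis test, however, uses the binary proportion.

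A reader might also take the similar phrase about confirmed pregnancy in 7.2.2.5.6 as a second instance. It is not shown to be an error, since stopping imaging in pregnancy may be intended.

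**What to change.** In the Grade 3 pancreatitis row for benefiting patients, replace the removal clause with: alpelisib must be permanently discontinued, with tumour and survival follow-up continuing per 4.3, 7.1.5, 7.1.8 and 7.1.9. If the sponsor intends both drugs to stop, write study treatment in place of alpelisib; the sponsor should say which.

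The cost is a few words, which can go into the next protocol amendment. No new data, analysis or listing is needed, because SAP 2.3.1, 2.4.1 and 2.8.1 already report reasons for leaving efficacy follow-up, reasons for stopping each drug, and adverse events leading to discontinuation. The sample size of 112 and the cut-off of 44 are unchanged.

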6.3.2 Follow-up for toxicities

All patients must be followed up for safety (adverse events and serious adverse events) for 30 days following the last dose of study treatment. Patients should have weekly follow-up for 30 days after discontinuation of study treatment or resolution of the AE to \leq grade 1, whichever occurs first. Post treatment follow-up (for safety) includes all study assessments appropriate to monitor the event.

Participants whose treatment is interrupted or permanently discontinued due to an adverse event or a clinically significant laboratory value must be followed until resolution or stabilization of the event, whichever comes first. Further guidelines and recommendations for the management of specific study treatment combination-induced toxicities are provided below.

6.3.2.1 Additional follow-up for selected toxicities

6.3.2.1.1 Management of pneumonitis/Interstitial lung disease

Alpelisib is associated with pneumonitis/interstitial lung disease. Closely monitor all subjects for signs and symptoms of pneumonitis.

All patients will be routinely asked about and observed for the occurrence of adverse events including new or changed pulmonary symptoms (consistent with lung abnormalities).

Patients who are suspected to have developed pneumonitis should interrupt alpelisib immediately (but may continue fulvestrant or letrozole if clinically indicated) and undergo appropriate imaging (high resolution CT scan) and broncho-alveolar lavage (BAL) and biopsy should be considered if clinically appropriate. Infectious causes of interstitial lung disease should be ruled out. Investigators should follow institutional practice for management of pneumonitis which generally includes treatment with high dose corticosteroids; antibiotic therapy should be administered concurrently if infectious causes are suspected. Consultation with a pulmonologist is highly recommended for any pneumonitis case during the study treatment. After ruling out infectious etiology and upon making a diagnosis of pneumonitis, permanently discontinue treatment with alpelisib and promptly initiate appropriate treatment and supportive measures.

Table 6-4 Management of pneumonitis

Pneumonitis (any grade)	Immediately interrupt alpelisib for any case of suspected pneumonitis. Fulvestrant or letrozole may be continued, if clinically indicated. Obtain appropriate imaging (high resolution CT scan) and consider BAL and biopsy if appropriate based on clinical judgment. See Section 6.3.2.1.1 for details of management of pneumonitis. Treatment for pneumonitis should be initiated based on institution guidelines and generally includes high dose corticosteroids; antibiotic therapy should be administered concurrently if infectious causes are suspected. Alpelisib should be permanently discontinued in all patients with confirmed pneumonitis

6.3.2.1.2 Guidelines for the treatment of study drug induced skin toxicity

Skin toxicity is an adverse drug reaction observed with PI3Ki agents.

Close monitoring of potential skin reactions will be performed at each planned visit and will be reported as an adverse event. The most frequent skin adverse events reported are: maculopapular rash (only a minority present acneiform rash); pruritus and dry skin. The onset is typically within the first 2 months of treatment start and is reversible with adequate co-medication and treatment interruption if needed. Skin reactions may improve over several weeks. If there are no new lesions or new areas of involvement developing, and if the appearance is changing color from red to pale or light brown, it is likely the eruption has begun to fade, and not considered active any longer. Consultation with a dermatologist is highly recommended for better assessment and management of alpelisib-induced skin toxicity at any grade, and mandated if severe cutaneous reaction like Stevens-Johnson-Syndrome, Toxic Epidermal Necrolysis, or Erythema multiforme or Drug Reaction with Eosinophilia and Systemic Symptoms (DRESS) is suspected.

Workup for skin toxicity events includes skin photography, a complete blood count with differential, and a full chemistry panel. A paired skin biopsy should be obtained (from both affected and an unaffected skin area) for local histopathology assessment to further assess the skin toxicity, especially to confirm suspected diagnosis of any severe cutaneous reactions.

In case of a Grade 3/4 skin toxicity, Novartis strongly recommends that photographs are taken and a skin biopsy is performed and stored at the site for source documentation. Antihistamines administered prior to rash onset may decrease incidence and severity of rash based on SOLAR-1 Study; therefore, at the Investigator's discretion, non-sedating antihistamines (e.g. cetirizine (Zyrtec[©]) fexofenadine (Allegra), loratadine (Claritin)) may be used as prophylactic treatment starting at Cycle 1 Day 1 to reduce severity of rash in all participants and especially for participants with a history of atopy such as allergic rhinitis, asthma, atopic dermatitis, or drug allergies. Antihistamine regimen should be continued for a minimum of 28 days after rechallenge with alpelisib.

Recommended therapies for skin toxicity events of all grades and as clinically indicated include:

- Consultation with a dermatologist should always be considered.
- Mid to high potency topical steroids: triamcinolone 0.01% or fluocinonide 0.05% twice daily for at least 28 days. Recommend spray, lotion, or cream preparation for ease of application on trunk. For scalp involvement, recommend a foam or solution preparation.
- *Gamma*-aminobutyric acid (GABA) Agonists: Gabapentin 300 mg every 8 hours, Pregabalin 50-75 mg every 8 hours (to adjust of renal impairment). Depending on participant's clinical condition, be aware of potential and common side effects observed with GABA agonists such as: somnolence, dizziness (both drugs) and peripheral edema (Gabapentin) among others adverse events.

For grade 4 skin events or any grade of severe cutaneous reactions (including SJS, TEN, EM, DRESS), alpelisib treatment must be permanently discontinued without any re-challenge.

If dry skin has been reported, it is recommended that patients with dry skin use mild and fragrance free soaps and detergents. According to the severity and BSA extension patients may apply mild moisturizers, e.g. ammonium lactate cream 12%.

Although preclinical experiments demonstrated that alpelisib has no potential phototoxic effect, patients should avoid sun exposure during treatment with alpelisib, especially when they already have experienced rash or other skin toxicities as the increased blood flow of the skin may worsen skin symptoms. Patients should be advised to take measures to protect themselves from direct exposure to sunlight, including the wearing of sunglasses as well as the regular use of sunscreen, hats, long-sleeve shirts and long pants when outdoors.

